4.4 Data Management and Security

For the purposes of this study, each subject will be assigned a unique randomly generated ID number, which will be used on all electronic data stored locally. A walk across file will be maintained to link the subject with the random ID number and will be stored in a separate location from all other data extracted. Only the study coordinator and PI will have access permissions to this file.

All electronic databases related to this protocol will be stored locally on a VA server in an entry controlled, locked room at the Jamaica Plain campus of the VA Boston Healthcare System. There are multiple levels of security to ensure the integrity and confidentiality of all data. The computer system operates entirely within the VA network, which is protected by a firewall maintained by the VA Office of Information Technology. Part of the maintenance of the VA server is that it is backed up regularly; therefore, all data related to this protocol will be routinely backed up and stored behind the VA firewall. Only authorized users can log on to the server. An additional layer of restrictions is at the file and directory level. Users can only access portions of the data to which they are entitled. Access to all data on the server is password protected. Access permissions will be removed and passwords will be changed whenever study personnel are no longer part of the research team.

All paper forms will be secured in a locked fireproof study cabinet. Only the PI will have keys to the study cabinet. All data will be kept indefinitely or until the law allows their destruction in accordance with the VA Record Control Schedule. Records will be destroyed, when allowed, in the following manner: paper records will be shredded and electronic records will be destroyed in a manner in which they cannot be retrieved. All suspected or identified information security incidents (e.g. theft or loss of data or unauthorized access) will be reported to the PI, ISO, and PO immediately upon suspicion by study staff.

To minimize data entry errors, all data collected on paper forms will be entered twice by a staff member using software that allows specification of valid responses for each entry field. Upon second entry of each record, the software will analyze each field to check for discrepancies in the two entries. Entry errors will be corrected on the spot and any errors requiring more extensive review will be deleted and re-keyed after the errors are resolved. In addition, the study coordinator will perform a careful quality assessment of all measures through logic and consistency checks and distributional assessment of overall distributions of responses. Data at follow-up exams will be compared to previous data for longitudinal consistency. Any patterns in missing or erroneous data will be discussed with the staff members collecting the data to determine the cause of the problem and what corrective measures will be taken. Databases will be carefully versioned so that all analyses can be clearly audited.

4.5 Statistical Analysis

Change in the Hamilton Rating Scale for Depression (HAM-D) was analyzed with the use of PROC MIXED (SAS) to estimate intervention effects based on a mixed-effects longitudinal model (40). The unstructured covariance model was used to allow for different variances at each time point (baseline, 6 months) and different correlations between outcomes for each pair of visits. The home-based exercise intervention program improved HAM-D score at the 6-month follow-up, as compared with the health education program with a between group difference of -3.4 points ($p < 0.05$; total $N = 40$). The standardized mean difference (SMD) was -0.6, which is between a medium and large effect. This SMD is very similar to that observed in a meta-analysis of major depression and exercise interventions in non-PD, which indicated a pooled SMD of -0.61 (15). However, we are not aware of any published data providing a minimal clinically important difference (MCID) on the HAM-D against which to compare our results.

References

1. Parkinson's Disease Research, Education and Clinical Centers. VA Establishes Six Parkinson's Disease Centers [online]. Accessed August 10, 2014.

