1. STUDY GOALS

Nonmotor symptoms in Parkinson's disease (PD) are thought to be present from the early stages of disease and are often more disabling and resistant to treatment than motor symptoms. One of the most important and serious of these symptoms is depression. However, there is no consensus on best pharmacological treatment for depression in PD as efficacy is lacking and there is much concern about polypharmacy and safety of various antidepressant medications. Therefore, it is essential that we characterize the effects of nonpharmacological interventions on depression in PD. A number of studies have shown significant benefits of exercise in reducing depressive symptoms. Emerging studies indicate similar benefits of exercise in the form of resistance training in limiting depression in older adults as well as in those with PD.

We propose to conduct a randomized, controlled trial of a novel program that uses resistance training coupled with real-time guidance delivered remotely in veterans 40 years of age or older with depression in PD. The recruitment goal of this VA RR&D SPIRE project was to recruit a total of 40 participants. The SPIRE award mechanism is intended to fund small pilot projects that lack preliminary data. Our aim was to determine whether there are differences in change on the Hamilton Rating Scale for Depression between patients in the resistance training intervention program and patients in a health education control program.

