4.1.2 Baseline Evaluation

We will administer the Structured Clinical Interview for DSM-IV (SCID) (31) and confirm the diagnosis of depression based on published criteria (32). Patients with confirmed depression will then complete the Hamilton Rating Scale for Depression (33). This measure will be repeated later as described in detail in Section 4.3. Half of the 40 participants will be randomized to each experimental arm.

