4.3 Outcome Data Collection

We will assess the Hamilton Rating Scale for Depression (HAM-D) (33) at baseline and 6 months at the Jamaica Plain campus of the VA Boston healthcare system with participants in an optimally medicated (on) dopaminergic state. HAM-D is the most widely used and accepted measure for evaluating depression severity (38). The 17-item version of the HAM-D results in scores ranging from 0 to 54, with higher scores representing more severe depression. The scale has been found to be sensitive to change in patients with PD (38).

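### Section 4.5 most naturally describes an unadjusted comparison of HAM-D change; a baseline-adjusted estimate should be reported, or an existing baseline constraint stated (minor).

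*Combined protocol and SAP*

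**What the plan says.** The aim in section 1 of the combined protocol and SAP is to learn "whether there are differences in change on the Hamilton Rating Scale for Depression between patients" in the two arms. Section 4.3 provides two assessments: "We will assess the Hamilton Rating Scale for Depression (HAM-D) (33) at baseline and 6 months". Section 4.1.2 places the baseline HAM-D at the baseline evaluation and allocates 1:1: "Half of the 40 participants will be randomized to each experimental arm".

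Section 4.5 is the whole statistical section and is written after the results were known. On the model it says "Change in the Hamilton Rating Scale for Depression (HAM-D) was analyzed with the use of PROC MIXED (SAS) to estimate intervention effects", from a mixed-effects longitudinal model, and then "The unstructured covariance model was used to allow for different variances at each time point (baseline, 6 months". Baseline is therefore part of the response vector. The section names no baseline covariate and does not say whether the arms' baseline means were free or held equal.

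The result is that the exercise program "improved HAM-D score at the 6-month follow-up, as compared with the health education program with a between group difference of -3.4 points", with p < 0.05 and total N = 40. On the standardized scale, "The standardized mean difference (SMD) was -0.6, which is between a medium and large effect". No SE, confidence interval or baseline HAM-D by arm is given.

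**The concern.** With two visits, an unstructured covariance and complete data, an arm-by-time contrast with free baseline means gives exactly the raw difference in mean change. Putting baseline among the responses does not by itself adjust for it. Adjustment comes from using baseline as a covariate or from forcing the arms to share a baseline mean, which randomization justifies.

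The unadjusted contrast is unbiased over repeated randomizations. The cost lies in the single randomization that took place. With 20 per arm, baseline means can differ by chance, and a change-score comparison carries part of that difference into the estimate. It also usually has a larger variance than the adjusted estimate. The baseline HAM-D is collected on every participant anyway, so the adjusted estimate is nearly free. Without baseline means by arm, a reader cannot tell how much of the -3.4 points, if any, comes from such an imbalance.

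**Working it through.** **Inputs from the documents.** Difference -3.4 points, SMD -0.6, p < 0.05, N = 40 (section 4.5); 20 per arm (section 4.1.2).

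**Assumptions, because the documents do not give the figures.** The SMD denominator is taken as the HAM-D SD at both visits; data are complete; the test is two-sided; r, the baseline to 6-month correlation, is varied.

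**1. The plan's own figure.** Implied SD = 3.4/0.6 = 5.67. With 38 df the critical t is 2.024, so p < 0.05 needs an SE of at most 3.4/2.024 = 1.680. That is an SD of change of at most 1.680/√(2/20) = 5.311. With equal visit SDs the SD of change is 5.667 × √(2(1 − r)), so the condition is r ≥ 1 − (5.311/5.667)²/2 = 0.56. The reported p-value therefore fits a change contrast if r is about 0.56 or more. Rounding of the SMD moves this threshold from 0.485 (SMD 0.65) to 0.631 (SMD 0.55). The p-value cannot be reproduced exactly, because r and the SE are not given.

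**2. Effect of baseline imbalance.** Let D0 and D6 be the between-arm differences at baseline and at 6 months, and k the ratio of the 6-month SD to the baseline SD. The change contrast is D6 − D0 and the adjusted estimate is D6 − rk × D0, so they differ by (1 − rk) × D0. One SE of D0 is 5.667 × √(2/20) = 1.79 points.

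**3. Precision.** The large-sample variance ratio, adjusted to change, is k²(1 − r²)/(1 + k² − 2rk). At k = 1 this is (1 + r)/2. Estimating the slope at N = 40 multiplies it by 37/36.

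**4. Results at k = 1, over values of r that fit p < 0.05:**

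| r | Shift for a one-SE imbalance, (1 − r) × 1.79 | Share of 3.4 | Variance ratio, large sample | Variance ratio × 37/36 | SE reduction at N = 40 |
|---|---|---|---|---|---|
| 0.56 | 0.79 | 23% | 0.78 | 0.80 | about 10% |
| 0.7 | 0.54 | 16% | 0.85 | 0.87 | about 7% |
| 0.8 | 0.36 | 11% | 0.90 | 0.925 | about 4% |
| 0.9 | 0.18 | 5% | 0.95 | 0.976 | about 1% |

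The shift can go either way. If the exercise arm started one SE higher, a change contrast of -3.4 corresponds to an adjusted -2.61 at r = 0.56 (-3.4 + 0.79). If it started one SE lower, the adjusted value is -4.19.

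**5. Unequal SDs, with 5.67 as the baseline SD.** At k = 1.3 and r = 0.7 the variance ratio is 1.69 × 0.51/(1 + 1.69 − 1.82) = 0.862/0.870 = 0.991, and × 37/36 it is 1.02, so there is no gain. At k = 0.8 and r = 0.56 it is 0.64 × 0.686/(1 + 0.64 − 0.896) = 0.590, a larger gain.

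**The case against.** The strongest reply is that nothing here is shown to be an error. A comparison of change matches the stated aim and is unbiased under randomization, and preferring an adjusted estimate is a choice about efficiency. That stands. So does the point that the gain may be small: at r = 0.9 it is about 1% of the SE, and it can vanish if HAM-D is more variable at 6 months than at baseline. No passage suggests that an imbalance occurred, and this is a 40-person pilot. What survives is that the better estimate needs only data already collected, and that section 4.5 makes a comparative efficacy claim with a p-value.

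A reader might go further in three ways that the documents do not support:

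- **That the tested contrast is unstated.** The results sentence refers to the score at 6 months, which could suggest a comparison of 6-month means. But section 1 and the opening of section 4.5 both speak of change, and the two visits are named. Together they largely indicate the contrast.
- **That the analysis was certainly unadjusted.** A model with equal baseline means also fits the wording, so lack of adjustment is an inference.
- **That p < 0.05 contradicts the SMD.** If 0.6 is exact and standardized on the SD of change, t = 0.6 × √10 = 1.897 and p = 0.065. But p < 0.05 needs an SMD of only 0.64, which rounds to 0.6, and with a visit SD as denominator the two agree once r reaches about 0.56.

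**Conclusion.** The concern holds as a minor one. Section 4.5 states no baseline covariate or equal-baseline constraint, and its most natural reading is the raw difference in mean change. Under equal visit SDs of 5.67, 20 per arm and complete data, a one-SE baseline imbalance would account for 5% to 23% of the reported difference over r = 0.56 to 0.9, and adjustment would cut the large-sample variance by 5% to 22%. These figures show what is possible; they do not measure an imbalance in this trial. They rest on an SMD denominator, an SD ratio and a correlation that the documents do not give. Adjustment could strengthen or weaken the result. Nothing here shows that -3.4 points or p < 0.05 is wrong, or that the finding is an artifact of imbalance.

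**What to change.** Report a baseline-adjusted difference with its 95% CI. Two routes serve: ANCOVA of 6-month HAM-D on arm and baseline HAM-D, or the same PROC MIXED model with unstructured covariance and equal baseline means (visit and arm-by-6-month terms, with no arm effect at baseline).

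If the fitted model already held baseline means equal, one sentence saying so is enough. If it did not, keep -3.4 as the original result and show the adjusted estimate beside it, labelled post hoc.

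The cost is a sentence or two in section 4.5 and at most one further model run. The limitation is that results are already reported, so an adjusted estimate added now carries only post hoc weight.

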3. PRELIMINARY STUDIES

We have experience successfully implementing a remote home-based resistance exercise training program in older veterans (age range, 50 to 94 years) (20). By the end of the 12-month program, 86% retention of the participants was achieved. This program, the Telephone-Linked Computer-based Long-term Interactive Fitness Trainer (TLC-LIFT), significantly increased lower extremity strength and decreased depressive symptoms over levels in the health education control arm. There were no serious adverse events related to the TLC-LIFT intervention. Further, there was virtually no difference in nonserious adverse events (musculoskeletal injury and discomfort) between the intervention and control groups.

The TLC-LIFT program uses advanced interactive voice response (IVR) technology, including speech-recognition software, to facilitate communication with TLC-LIFT. The TLC-LIFT program provides verbal instructions on what exercises to do and how to do them, guiding the participants through the exercises as they perform them in their home. The TLC-LIFT system asks the participant to begin a given exercise and to count each repetition out loud. Voice recognition of each counted repetition allows the system to monitor the number of repetitions for each exercise. Because TLC-LIFT is fully automated and administered by telephone in the participant's home, TLC-LIFT offers great flexibility and sufficiently low cost to continue indefinitely. To facilitate this approach, participants are supplied with a wireless headset (with microphone) that connects with their existing phone, thus allowing for hands-free communication with TLC-LIFT as they exercise. TLC-LIFT utilizes speech-recognition technology that we have customized to recognize wide variations in speech clarity, in addition to variations in speech during exercise (e.g., variations counting repetitions out loud due to changes in breathing patterns). Furthermore, TLC-LIFT facilitates interactive communication (e.g., "Are you ready to set

a higher goal for your next exercise?") tailored to each individual to optimize engagement and a person-centered approach. Participants are provided with an illustrated booklet that converts to a desktop easel, allowing them to see the exercises while simultaneously listening to the audio instructions.

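### Does the SMD of -0.6 in Section 4.5 contradict the printed p < 0.05 with 20 participants per arm?

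*Combined protocol and SAP*

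**What the plan says.** Section 1 gives the aim as finding out whether there are "differences in change on the Hamilton Rating Scale for Depression between patients in the resistance training intervention program" and those in the health education control. Section 4.3 fixes the schedule: "We will assess the Hamilton Rating Scale for Depression (HAM-D) (33) at baseline and 6 months". Section 4.1.2 sets equal allocation: "Half of the 40 participants will be randomized to each experimental arm", that is, 20 per arm.

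Section 4.5 is written in the past tense and reports the result. HAM-D change was analysed with a mixed-effects longitudinal model in PROC MIXED. The covariance was unstructured, allowing different variances at the two times and "different correlations between outcomes for each pair of visits". The programme "improved HAM-D score at the 6-month follow-up, as compared with the health education program with a between group difference of -3.4 points", with p < 0.05 and total N = 40 in the same parenthesis. Then: "The standardized mean difference (SMD) was -0.6, which is between a medium and large effect".

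Section 4.5 does not say which SD forms the SMD, whether -3.4 contrasts change scores or 6-month scores, or whether it is baseline-adjusted. It gives no SE, confidence interval, exact p, sidedness, numbers per arm, or number with a 6-month HAM-D.

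**The concern.** This is the only efficacy result in the document, and a reader's natural first check appears to fail. A difference of 0.6 SD between two groups of 20 gives a two-sample t of about 1.90, short of the 2.02 needed for two-sided significance at 5%. On that reading the 95% confidence interval for the -3.4 points just includes zero, and the statement that the programme improved HAM-D would lack support at the usual level.

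Two points add to the unease. The outcome is called change in Section 1 and at the start of Section 4.5, but the result sentence speaks of the score at 6 months, so the relevant SD is uncertain. And N = 40 equals the number to be randomised. If some participants lacked a 6-month score, the simple check becomes harder to pass. The team's earlier study reports "By the end of the 12-month program, 86% retention of the participants was achieved", so some loss is plausible.

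**Working it through.** **Inputs.** From Section 4.5: difference -3.4, SMD -0.6, p < 0.05, total N = 40. From Section 4.1.2: 20 per arm. Not in the documents, so assumed over a range: the baseline to 6-month correlation r, and the number with a 6-month score.

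**1. Literal reading.** Take the SMD on the SD of the tested quantity, unadjusted, two-sided:

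- t = 0.6 / sqrt(1/20 + 1/20) = 0.6 / 0.3162 = 1.897, df = 38, p = 0.065.
- Implied SD = 3.4 / 0.6 = 5.67; SE = 5.67 × 0.3162 = 1.79.
- 95% CI = -3.4 ± 2.024 × 1.79 = -7.03 to 0.23.
- SMD needed for p < 0.05: 2.024 × 0.3162 = 0.640, which for -3.4 points means an SD of at most 5.31.

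So the printed p < 0.05 is not reproduced if -0.6 is taken as exact on this reading.

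**2. Rounding.** A printed -0.6 stands for 0.55 to 0.65 in absolute value.

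| Absolute SMD | Two-sided p, 20 per arm |
|---|---|
| 0.55 | 0.090 |
| 0.60 | 0.065 |
| 0.641 | 0.0497 |
| 0.65 | 0.047 |

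The range straddles 0.05. With N = 40 as printed, the figures can agree even on the literal reading, though only in the top tenth or so of the rounding interval.

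**3. SMD on a raw-score SD, change contrast** (equal variances at the two visits). The SD of change is the raw SD × sqrt(2(1 - r)), so t = 1.897 / sqrt(2(1 - r)).

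- r = 0.3: p = 0.117. r = 0.5: p = 0.065. r = 0.6: p = 0.040. r = 0.7: p = 0.019.
- p < 0.05 when r exceeds 1 - (0.6/0.640)²/2 = 0.56.
- At r = 0.7 the SD of change is 5.67 × sqrt(0.6) = 4.39, the SE is 1.39, and the CI is -6.21 to -0.59.

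**4. SMD on a raw-score SD, baseline-adjusted contrast.** The residual SD is the raw SD × sqrt(1 - r²), so t = 1.897 / sqrt(1 - r²), df = 37.

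- r = 0.3: p = 0.054. r = 0.4: p = 0.045. r = 0.5: p = 0.035.
- p < 0.05 when r exceeds about 0.35.

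**5. One-sided p.** For 0.6 with 20 per arm it is 0.033. The text does not state sidedness.

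**6. Missing 6-month scores.** On the literal reading with complete cases, the critical SMD is 0.649 for 20 and 19, 0.658 for 19 and 19, and 0.699 for 17 and 17 (about 86% of 40). With 19 per arm even 0.65 gives p = 0.053. That is not a general bar, because a mixed model keeps participants who have only a baseline score. For the 6-month contrast with 19 of 20 per arm observed, the variance per arm (in SD units) is (1 - r²)/19 + r²/20. The critical SMD is then 0.6487 at r = 0.7 and 0.6462 at r = 0.8, both below 0.65; the crossing is at r of about 0.64. The raw-SD readings in steps 3 and 4 also survive some loss: with 17 per arm and an SMD of 0.60, the change contrast needs r above 0.63.

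**7. Covariance wording.** Two visits give one pair and one correlation. An unstructured 2 × 2 covariance has two variances and one covariance however the sentence is phrased, so no figure is affected.

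**The case for a change.** The best case for acting is that the readings lead to opposite conclusions and the text chooses none. On the literal reading the interval is -7.03 to 0.23. On a raw-score SD with a change contrast and r = 0.7 it is -6.21 to -0.59. A reader cannot recover the SE or tell whether two-sided significance holds, yet the text says the programme improved HAM-D and sets the SMD beside a meta-analytic -0.61. Supplying the SE, interval and exact p would cost little if -3.4 is the contrast already fitted.

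Much of this stands. The omissions are real, and anyone quoting the result should ask for those figures. What does not follow is that a stated result or an analysis choice should change. The result is not without a sample size, since N = 40 is printed beside it; what is missing is the split by arm and the number with a 6-month score. The 86% retention comes from a 12-month programme in older veterans and says nothing direct about loss in this 6-month trial. Rewording the claim of improvement would be justified only by an exact two-sided p of 0.05 or more, and nothing in the documents shows that. Whichever contrast was fitted, the model and the data stay the same.

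**Conclusion.** No change to the plan follows. The arithmetic behind the worry is correct: an SMD of exactly 0.6 on its own SD, with 20 per arm and no adjustment, gives a two-sided p of 0.065 against a critical SMD of 0.640. But the printed figures are compatible with p < 0.05 through rounding (p down to 0.047), through a raw-score SD with a change contrast (r above about 0.56), or through a raw-score SD with a baseline-adjusted contrast (r above about 0.35). The two correlation thresholds assume equal variances, 20 per arm and an SMD of 0.60; the correlation itself is not in the documents. The literal reading is therefore not established, and no inconsistency is demonstrated.

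What remains is a minor reporting gap in a pilot trial's result paragraph. Naming the contrast and the SD, and giving the SE, interval, exact p and the number per arm with a 6-month score, is ordinary reporting. An analyst holding the data and the model fit can supply it without altering design, model or data. The phrase about pairs of visits is stock wording with no numerical consequence.

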2.2 Exercise and Depression

A recent meta-analysis of exercise interventions and major depression indicated a pooled standardized mean difference (SMD) of -0.61 (95% CI, -0.88 to -0.33), based on 10 trials and 758 participants. Improvement of depressive symptoms was greater with strength training (SMD -0.96) than with aerobic training (SMD -0.52) (15). Similarly, a recent Cochrane review examined the effectiveness of exercise compared to no intervention for depression in adults (16). The pooled SMD for resistance exercise met the criteria for a large clinical effect (SMD -1.03, 95% confidence interval [CI], -1.52 to -0.53). This effect was greater than that observed with aerobic training (SMD -0.55, 95% CI -0.77 to -0.34) or with mixed aerobic and resistance exercise.

A recent study revealed evidence that progressive strengthening exercises can reduce depression in patients with PD (17). Thirty-one patients with mild PD were randomly assigned to an early start group consisting of 48 weeks of exercise (weeks 1 to 48) or a delayed start group consisting of 24 weeks of exercise (weeks 24 to 48). Both groups exercised for one hour, three days per week. At 48 weeks, both groups experienced improvements in depression, as measured by the Beck Depression Inventory. Importantly, the early start group experienced significantly ($p=0.04$) greater improvements in depression, as compared with the delayed start group. This suggests that higher doses of strengthening exercises – both longer duration exercise and greater progression of exercise intensity over time – contributed to larger beneficial effects. Exercise-related increases in neurotrophic factors (e.g., glial-derived neurotrophic factor [GDNF] and brain-derived neurotrophic factor [BDNF]) may represent underlying biological mechanisms consistent with these effects. Coelho et al. (18) showed significant increases in plasma concentrations of BDNF after a 10-week strength training program in community-dwelling elderly women. A recent clinical trial found that strength training, but not aerobic training, significantly increased plasma BDNF levels and reduced depressive symptoms (change in Geriatric Depression Scale scores: -0.85 [strength training], -0.54 [aerobic training]) in elderly women (19).

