4. RESEARCH DESIGN AND METHODS

4.1 Participants for the Randomized, Controlled Trial

We will conduct an RCT of our home-based resistance training program (TLC-LIFT) in patients with depression in PD. Forty patients will be randomized to the TLC-LIFT program for 6 months or to a health education control program for 6 months. Patients with depression in PD who meet eligibility criteria will be recruited into this study. Specific inclusion criteria will include a physician diagnosis of idiopathic, typical PD; at least 2 of the 3 cardinal signs of PD (resting tremor, rigidity, bradykinesia); response to dopaminergic medication; absence of secondary causes of Parkinsonism; a diagnosis of major depression, dysthymic disorder, or minor depressive disorder; and an age of 40 years or older. Exclusion criteria will include a diagnosis of angina pectoris (unless symptomatically resolved post-revascularization); a history of myocardial infarction (MI) within 6 months, or remote (>6 months) MI with current ischemia on an exercise stress test; and a history of ventricular dysrhythmia requiring current therapy, or current atrial fibrillation without adequate rate control (resting HR <90).

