4.2.2 Health Education Control

The group randomized to receive health education will serve as an attention control. Participants will be

asked to use the health education control system 3 times a week, which will deliver general information about a variety of health topics including content on exercise. This system, similar to the TLC-LIFT system, provides auditory instructions/content via the participant's home telephone. The health education control system uses advanced IVR technology, including speech-recognition software, to facilitate communication with the system. There are opportunities for participant interaction while the content is delivered by the system, for example, the participant can request subtopics about which they desire more information while skipping others of less interest. Near the end of the baseline visit, the initial health education session is completed with a staff member who has experience working with patients with PD.

During the first four weeks of the intervention, content on exercise based on the Fitness Counts program developed by the National Parkinson Foundation (Chapters 3 & 4) (37) will be presented focusing on the benefits of exercise for persons with PD (1 session), the types of exercises important for persons with PD (1 session), principles of stretching and strengthening exercises (2 sessions), descriptions of safe stretching and strengthening exercises for persons with PD (6 sessions), and strategies to overcome barriers to exercise (2 sessions). Participants will be provided with illustrations of the exercise program with written instructions to accompany the auditory content. Subsequently, during each session, participants will select a topic from 4 content areas: common symptoms, medical conditions, preventive medicine topics, and tips for healthy living with PD. These PD-specific tips include mobility strategies, such as strategies for moving from lying down to a sitting position, and from sitting to standing position, and tips to help with performance of daily activities including organization of the physical environment and reducing time pressure. A similar approach as described above (see Section 4.2.1) will be used in the control group to encourage and maintain study adherence.

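### Does Section 4.5 use the wrong literature benchmark when it sets its SMD of -0.6 beside -0.61 for all exercise, and not beside -0.96 for strength training?

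*Combined protocol and SAP*

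**What the plan says.** Section 4.5 reports a "between group difference of -3.4 points ($p < 0.05$; total $N = 40" and restates it on a standardized scale: "The standardized mean difference (SMD) was -0.6, which is between a medium and large effect". It next compares that SMD with one published figure, the pooled -0.61 of reference 15: "This SMD is very similar to that observed in a meta-analysis of major depression and exercise interventions in non-PD". It closes by saying that no published minimal clinically important difference for the HAM-D is known to the investigators.

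Section 2.2 gives more detail on the same source. The overall result is introduced as "A recent meta-analysis of exercise interventions and major depression indicated a pooled standardized mean difference (SMD) of -0.61 (95% CI, -0.88 to -0.33", from 10 trials and 758 participants, and is then split by type of exercise: "Improvement of depressive symptoms was greater with strength training (SMD -0.96) than with aerobic training (SMD -0.52) (15". A second review, of exercise against no intervention, supplies another resistance figure: "The pooled SMD for resistance exercise met the criteria for a large clinical effect (SMD -1.03, 95% confidence interval [CI], -1.52 to -0.53".

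Section 4.1 leaves no doubt about the type of exercise under test: "We will conduct an RCT of our home-based resistance training program (TLC-LIFT) in patients with depression in PD". The comparator in Section 4.2.2 is an attention control whose first four weeks include exercise content, among it "descriptions of safe stretching and strengthening exercises for persons with PD (6 sessions".

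**The concern.** The programme is resistance training, and the document holds a strength-training SMD from the very reference that Section 4.5 cites. Section 4.5 leaves it out and uses the all-exercise average, which happens to fall almost exactly on the trial's result. Section 2.2 itself treats type of exercise as important, since it reports larger effects for strength or resistance work than for aerobic work from two reviews.

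A reader of Section 4.5 alone could therefore conclude that the programme did about what the literature predicts. A reader who turned to the strength figure would see a point estimate about a third smaller. As no minimal important difference is offered, the comparison with other studies carries some of the interpretation. If the benchmark had been picked because it agreed, the impression of replication would come from that choice and not from the data.

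**Working it through.** **Inputs.** From Section 4.5: SMD -0.6, difference -3.4 points, N = 40. From Section 4.1.2: half of the participants in each arm, so n = 20 per arm. From Section 2.2: pooled -0.61 (95% CI -0.88 to -0.33); strength -0.96 and aerobic -0.52, neither with a CI; resistance -1.03 (95% CI -1.52 to -0.53).

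**The plan's own figure.** The SMD cannot be reproduced, because no SD is given. It implies a standardizing SD of 3.4/0.6 = 5.67 points. Rounding of both figures allows 3.35/0.65 = 5.15 to 3.45/0.55 = 6.27. The section does not say whether this is a baseline, follow-up or change-score SD.

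**Point estimates side by side** (trial SMD anywhere from -0.55 to -0.65 after rounding):

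| Benchmark | Gap from -0.6 | Range from rounding | Ratio |
|---|---|---|---|
| All exercise, -0.61 | 0.01 | up to 0.06 | 0.60/0.61 = 0.98 |
| Aerobic, -0.52 | 0.08 | 0.03 to 0.13 | 0.60/0.52 = 1.15 |
| Strength, -0.96 | 0.36 | 0.31 to 0.41 | 0.60/0.96 = 0.625 |
| Resistance (second review), -1.03 | 0.43 | 0.38 to 0.48 | 0.60/1.03 = 0.58 |

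So the sentence in Section 4.5 is arithmetically right about the figure it names, and the strength figure is clearly larger as a point estimate.

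**Can the trial tell these benchmarks apart?** Unadjusted, SE = sqrt(2/n + d²/(4n)) = sqrt(2/20 + 0.36/80) = 0.323. The approximate 95% interval is -0.6 ± 1.96 × 0.323, or -1.23 to 0.03. The reported model uses the baseline value, so its interval should be narrower, and p < 0.05, if two-sided, requires that it exclude zero. As a sensitivity check, take SE = sqrt((2/n)(1 − ρ²)), where ρ is an assumed correlation between baseline and 6 months, with a t quantile of 2.026 on 37 degrees of freedom:

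- ρ = 0.4: SE = 0.290, interval -1.19 to -0.01.
- ρ = 0.7: SE = 0.226, interval -1.06 to -0.14.

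All three intervals contain both -0.61 and -0.96. To exclude -0.96 the half-width must fall below 0.36, so the SE must be below 0.36/2.026 = 0.178. That needs ρ above sqrt(1 − 0.178²/0.1) = 0.83.

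**Direct comparisons, unadjusted.** Against -0.96 treated as fixed: z = 0.36/0.323 = 1.11, p = 0.27. Against -1.03, whose SE is (1.52 − 0.53)/3.92 = 0.253: z = 0.43/sqrt(0.323² + 0.253²) = 1.05, p = 0.29. Treating -0.96 as fixed overstates the evidence, because its own uncertainty is not quoted.

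**How close a match is the strength figure?** It matches on type of exercise but not on population. Reference 15 concerns major depression outside Parkinson's disease, whereas Section 4.1 also admits dysthymic and minor depressive disorder. Section 2.2 does not give the comparator behind -0.96. The -1.03 review compared exercise with no intervention. Here, of the 1 + 1 + 2 + 6 + 2 = 12 control sessions in weeks 1 to 4, 2 + 6 = 8 dealt with stretching and strengthening. The pooled -0.61 shares the population mismatch, but it comes with a CI, a trial count and a sample size.

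**The case for a change.** The best case for a change is that the omission flatters the result at almost no cost to repair. Both figures come from one reference, the document stresses that strength training does better, and Section 4.5 shows only the figure that agrees. No choice of SD rescues the wording for both: scaling -0.6 up to -0.96 needs a factor of 0.96/0.60 = 1.6, which would carry it away from -0.61. Two or three sentences would put the larger figure in view.

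The omission is real and that scaling argument stands. Three further supports are weaker.

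- The literature comparison is not the section's only yardstick, since it also labels the effect as lying between medium and large.
- That -0.96 falls outside the CI of the pooled -0.61 does not show that the two benchmarks conflict. The strength estimate belongs to the same meta-analysis, and its own uncertainty is not quoted.
- The size of the shortfall, whether as a percentage or in HAM-D points, rests on an SD that the section does not identify. It might change if the meta-analysis standardized differently.

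**Conclusion.** No change is needed. The comparison in Section 4.5 is true as a statement about point estimates and is labelled as concerning exercise interventions outside Parkinson's disease. It does not claim to match strength training, and no section sets -0.96 as a target. The strength figure is open to any reader in Section 2.2 under the same citation. Using the overall estimate, which is the better documented of the two, is a fair choice.

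The point estimate is 0.36 below the strength figure (0.31 to 0.41 from rounding), taking the printed SMDs as comparable. The approximate intervals at 20 per arm contain both benchmarks unless the baseline correlation exceeds about 0.83. The data therefore establish neither agreement with -0.61 nor a shortfall from -0.96. These intervals assume complete data on 40 patients and an SMD standardized by a common between-patient SD.

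An author who wished could print -0.96 beside -0.61 and say that only point estimates are compared, in a different population and against a different control. That would be added context, with the design, model, estimate and p value unchanged.
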